#### *Study secondary endpoints*

1. Healing time (in which healing is represented by a lasting and complete re-epithelialization);
2. Reduction of the lesion surface in both arms, during the 20 weeks, measured in absolute terms (square centimeters) and as % of the initial size;
3. Quality of life (QoL), evaluated both with specific questionnaires (EuroQoL-5D) and generic questionnaires (Wound-QoL);
4. Perception of pain measured with a subjective analogue rating scale (VAS);
5. Assessment of the costs related to the two arms in the perspective of the National Health System, NHS (considering only direct health costs) and in the perspective of the Society (considering beyond direct health costs, direct non-health costs and indirect costs);
6. Patient's satisfaction with the EmoLED therapy, assessed by administering specific questionnaires;
7. Appreciation, complexity and usefulness of the EmoLED therapy by the operators assessed through the administration of specific questionnaires;
8. Security of treatment (number of Adverse Events in the two groups);
9. Evaluation of the cost-effectiveness of using EmoLED for the treatment of ulcers.

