#### *Direct and indirect cost questionnaires (Patient, Caregiver and Operator) (Annexes H, I)*

Cost-specific questionnaires will be administered to patients and the main caregiver (if present) at the last visit with the aim of identifying the resources absorbed by the patients (and their caregivers) treated in the two approaches.

The consumption of resources will be assessed by collecting information aimed at quantifying direct health costs (visits, hospitalizations, access to the emergency room, use of medicines, etc.), direct non-health costs (informal care, transport costs and accommodation per visit, etc.) and indirect costs (loss of productivity of the patient and of the caregiver/s) and considering both the costs associated with adherence to treatment taking the last visit as "standard event", and the costs associated with complications and events relating the ulcer, that determined the need of treatments/examinations and/or medical evaluations. The principal investigator will also be given a questionnaire to determine the costs incurred by their structure for the management of patients with leg ulcers.

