### **Statistical analysis**

Demographic and clinical data will be presented in tables and graphs in the form of frequencies and percentages for categorical variables, mean, standard deviation, median and interquartile range for continuous variables, differentiating by reference population and treatment group.

In the first analysis a qualitative comparison between the treatment groups will be carried out (healed/not healed) through the test  $\chi^2$  or the exact test of Fisher in the case of counts of less than 5. The results will be presented in contingency tables and bar charts.

A quantitative comparative statistic between treatment groups will then be performed by comparing the percentage reduction in the area of injury, the variation in quality of life level (QoL) and the variation in pain perception (VASS) through Mann-Whitney's nonparametric test.

The choice to perform a non-parametric analysis lies in the low sample size and therefore it is preferred to have more conservative significance values. The results will be presented in tables with median and interquartile interval in the two groups with its p.value and graphically through the box plot.

To analyze the internal and time-related differences between groups, Friedman's non-parametric test for the outcome variables will be performed.

Generalized linear models (GLM) will be used to investigate whether differences between the two groups are influenced in a confusing way by demographic, clinical covariates, pre-treatment measurement, and to measure their impact which will allow us to understand which variables they include on the outcome and will also allow us to analyze the differences between the equal groups of these covariates.

For the comparison about recovery time, since the study is based on the principle of "intention to treat" and therefore there is no caesura, it will be performed by comparing the average recovery times through the non-parametric test of Mann-Whitney.

Then a descriptive statistic will be made through tables with frequencies and percentages, and bar charts of the treatment satisfaction indices in patients and operators. In addition, adverse events in both groups will be described, if present.

Due to the generally asymmetric nature of the cost distribution, the comparison of the costs associated with the two treatment arms, both from the perspective of the SSN and the Company, will be carried out using the non-parametric U test of Mann-Whitney.

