Non-generalized linear regression models will be used to assess differences between groups, net of confounding factors.

The cost effectiveness of the two treatments in the time horizon of the study will be assessed by calculating the incremental cost effectiveness ratio (ICER) and expressed in terms of incremental cost for "quality adjusted life years" QALY.

Extrapolation of the results of the cost-effectiveness assessment by simulating longer time horizons will be carried out considering decision models (e.g. Markov models) and, where appropriate, integrating the data collected in the study with literature and/or evidence from other studies. All significance tests will have a statistically significant  $p < 0.05$  value. The analysis will be carried out with the open source software R Commander (v. 2-2.0).

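### The stated cost comparison is a rank test, which does not address the difference in mean cost that the payer and societal questions and the plan's own ICER require

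*Protocol*

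**What the plan says.** Two of the nine secondary endpoints are economic. Endpoint 5 is "Assessment of the costs related to the two arms in the perspective of the National Health System, NHS", and also from the societal perspective. Endpoint 9 is "Evaluation of the cost-effectiveness of using EmoLED for the treatment of ulcers".

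The Statistical analysis section fixes the method for endpoint 5. It opens with "Due to the generally asymmetric nature of the cost distribution, the comparison of the costs associated with the two treatment arms" and says that this comparison, for both perspectives, "will be carried out using the non-parametric U test of Mann-Whitney".

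The next sentence reads: "Non-generalized linear regression models will be used to assess differences between groups, net of confounding factors". It does not name the outcome. The section then plans to assess cost-effectiveness by "calculating the incremental cost effectiveness ratio (ICER) and expressed in terms of incremental cost for" QALYs gained, with extrapolation by decision models.

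The section on direct and indirect cost questionnaires lists what is counted, including "direct health costs (visits, hospitalizations, access to the emergency room, use of medicines, etc", together with the costs of complications and ulcer-related events.

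**The concern.** The Mann-Whitney test asks whether a randomly chosen patient in one arm tends to cost more than a randomly chosen patient in the other. A health service or a society pays the mean cost multiplied by the number of patients, and an ICER divides a difference in mean cost by a difference in mean QALYs. Skewness makes a normal-theory test on means less reliable at 20 per arm, but it does not change the question from means to ranks.

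The two answers can part when the cost distributions differ in shape. Ranks give a very expensive patient little more weight than a moderately expensive one, whereas the mean gives that patient full weight. Suppose EmoLED adds some cost to every treated patient and there are fewer rare, expensive events of the kind the cost questionnaires count. The rank test may then report EmoLED as dearer while its mean cost is lower. Endpoint 5 and the numerator behind endpoint 9 would disagree, and the protocol does not say which governs.

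**Working it through.** **Inputs from the protocol.** 20 patients per arm (Sample number); significance at p < 0.05 (Statistical analysis), taken here as two-sided. The protocol gives no cost means, spread or event rates and no power, so there is no figure of its own to reproduce. Every cost below is an assumption.

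**1. Can the two answers conflict? A fixed example, 20 per arm.**
- Control: 16 patients evenly spaced from 2,000 to 3,000 (mean 2,500) and 4 at 12,000. Mean = (16 × 2,500 + 4 × 12,000) / 20 = 4,400; median 2,633.
- EmoLED: 19 patients evenly spaced from 2,800 to 3,800 (mean 3,300) and 1 at 12,000. Mean = (19 × 3,300 + 12,000) / 20 = 3,735; median 3,328.
- Mean difference = 3,735 − 4,400 = −665, so the ICER numerator is negative.
- Mann-Whitney: U = 312.5 out of 20 × 20 = 400, p = 0.002, in the direction of EmoLED being dearer.

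The conflict is therefore possible.

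**2. When does it not arise?** With lognormal costs of the same shape in both arms (log-SD 0.8), the U test rejects in 5.0% of trials when the arms are equal. No significant result had the opposite sign to the sample mean difference, either with equal arms or with one arm 20% cheaper.

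**3. How often, under assumed costs?** Each patient's cost is a lognormal routine cost plus, with some probability, a 12,000 event.

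*Scenario 1.* Routine cost 3,000 (control) v 3,600 (EmoLED); event in 15% v 5%. True means: 3,000 + 0.15 × 12,000 = 4,800 and 3,600 + 0.05 × 12,000 = 4,200, so EmoLED saves 600. Only the CV of routine cost is varied:

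| Routine-cost CV | U test: EmoLED significantly dearer | Significantly dearer and sample mean lower, same trial |
|---|---|---|
| 20% | 36% | 13% |
| 40% | 9% | 0.9% |
| 60% | 5% | 0.1% |
| 80% | 3% | about 0% |

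The last column counts trials in which the test contradicts the sign of that trial's own ICER numerator.

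*Scenario 2.* Routine cost 3,000 v 3,400; event in 20% v 5%. True means 5,400 v 4,000. Significantly dearer: 10%, 2%, 1% and 1% at the same four CVs. Same-trial contradiction: 4% at CV 20% and 0.3% at CV 40%. From CV 40% upward, the U test says cheaper more often than dearer.

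**4. Other assumptions.** Here routine cost is 2,500 (median, log-SD 0.3), EmoLED adds a flat 400 to 1,200, and an event of about 12,000 falls from 15–25% to 5%. EmoLED is then truly cheaper by about 100 to 2,200. The U test says significantly dearer in 3% to 79% of trials, with a lower sample mean in the same trial in 1% to 32%. The rate grows with the flat added cost, and step 3 shows that it shrinks quickly as routine costs become more variable.

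**The case against.** Four points have force.

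- **Mean-based estimates are already planned.** The ICER needs a mean cost difference, and the regression sentence directly follows the cost sentence, so it may supply an adjusted one. It would be wrong to infer that mean cost is absent. What stands is that the regression names no outcome and the U test remains the stated cost comparison.
- **The protocol does not describe the mechanism that produces the conflict.** A reader might infer that the sponsor expects savings from prevented complications and that the U test would miss that very benefit. The rationale section does not say so: it hopes for fewer outpatient and home visits. Such a saving would lower routine cost, where ranks and means usually agree. Hospitalisations and complications are listed as cost items, not as events that EmoLED is expected to reduce.
- **The high error rates need nearly uniform routine costs.** The 36% holds at a CV of 20% and falls to 9% at 40%. A reader might also pair that 36% with the 70% of trials in which the sample mean favours EmoLED and conclude that conflict is frequent. Counted in the same trial, it is 13% at CV 20% and under 1% from CV 40%.
- **The replacement will often be inconclusive.** A percentile-bootstrap interval would detect the true saving in only about 9% of trials in scenario 1 and about 23% in scenario 2 (at CV 20%).

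A statistical analysis plan may settle the form of the interval, so its absence from the protocol is not counted here. The choice of a rank test as the cost comparison is written into the protocol and is open to comment.

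**Conclusion.** The point holds as a mismatch between the stated test and the quantity wanted. Skewness is a reason to be careful about how the uncertainty of a mean difference is computed; it is not a reason to test something else. A conflict in direction between the U test and the ICER numerator is possible, but only if the arms' cost distributions differ in shape. How often it would occur cannot be fixed from the protocol: under scenario 1 it runs from 13% of trials down to about 0% as the routine-cost CV goes from 20% to 80%, and it can be higher if EmoLED adds a large flat cost to tightly clustered routine costs. The documents do not support saying that the cost conclusion will be wrong, or that it probably will be. This is a minor correction to a secondary endpoint in a 40-patient proof-of-concept trial, and the primary healing endpoint is untouched.

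**What to change.** In the Statistical analysis section:

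1. For each perspective, make the cost comparison the difference in arithmetic mean cost per patient, with a bootstrap 95% CI.
2. State that this same difference is the numerator of the ICER.
3. Name cost as the outcome in the regression sentence, if that is what is meant, and have that model estimate the same mean difference, adjusted.
4. Keep medians and the Mann-Whitney test for costs as description only.

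This changes wording and needs no new data. The price is that the interval will be wide and often inconclusive at 20 per arm. It would, however, be a usable input to the planned decision models, which a rank-test p-value is not.

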## Data publication policy

At the end of the clinical study and of the related analysis about the obtained results, these will be made available anonymously and aggregated in full respect of the protection of the right to privacy, in accordance with Regulation no. 2016/679 (GDPR, General Data Protection Regulation), for publication in national or international journals, or for presentation by investigators at scientific conferences and in medical journals. For the writing of any publications concerning the study in question, may be used professional medical writers who will write manuscripts on behalf of the company and for which the company undertakes to ensure analogous compliance with current legislation.

After the conclusion of the study, the sponsor will be responsible for drawing up the final report of the clinical trial in the manner and timing prescribed in the current legislation regarding clinical investigations; external consultants of the sponsor, experts in this field, may be involved in the preparation of the final report.

